10.5.3.5 Poppy and Sesame Seeds

Participants will be advised that they must not eat food containing poppy or sesame seeds for 3 days before each visit to the Clinical Unit, as consumption of poppy seeds can lead to a positive opiate result in the drugs of abuse test.

10.5.4 Other Life-Style Restrictions

10.5.4.1 Strenuous Exercise

Strenuous exercise must be avoided completely from 3 days before receiving the first dose of IMP until completion of the Day 84 visit.

10.5.4.2 Blood Donation

Participants will be advised that they should not donate blood for at least 3 months after receiving the last dose of IMP (Day 42).

10.5.4.3 Travel Restrictions

Participants will be advised that they should not travel outside of the UK until a stool sample cultured for *Salmonella* produces a negative result to confirm that shedding of the presumed vaccine strain(s) has ceased.

10.5.5 Removal of Participants from Therapy or Assessment

Each participant will be informed of his/her right to withdraw from the study at any time and for any reason.

An Investigator will withdraw a participant from the study at any time for any of the following reasons:

- If a participant experiences a serious or intolerable AE, that prevents him/her from continuing participation in the study.
- If a participant incurs a significant protocol violation which impacts on his/her safety or the scientific integrity of the study (this will be discussed on a case-by-case basis with the Sponsor).
- At the request of the Sponsor.
- If it is considered that the participant's health is compromised by remaining in the study or the participant is not sufficiently cooperative.
- If a participant is lost to follow-up.

Participants who meet one or more of the following stopping criteria will receive no further doses of the study vaccine but will be followed up for safety:

- Severe systemic reaction, e.g., anaphylaxis.
- Persistent febrile reaction ($\geq 38.5^{\circ}\text{C}$ for ≥ 12 hours) at the Investigator's discretion
- SAE related to the study agent (serious adverse reaction (SAR) or suspected unexpected serious adverse reaction (SUSAR))

The medical safety of the participant is of paramount importance when discussing study continuation.

The reasons for any participant withdrawal will be recorded on the study completion form of the electronic case report form (eCRF).

If a participant is withdrawn or chooses to withdraw from the study for any reason every possible effort will be made to perform the evaluations described for the post-study follow-up (see [Table 10.7.1](#)). The data collected from withdrawn participants will be included in the study report.

In the event of any abnormalities considered to be clinically significant, participants will be followed up with appropriate medical management until values are considered to be clinically acceptable. Referral or collaborative care will be organised if considered necessary.

A total of 45 participants are required to complete the study. Participants who withdraw from the study before receiving any IMP will be replaced. Participants who are withdrawn from the study due to significant drug-related AEs will not be replaced. Replacement of all other participants withdrawn from the study after receiving IMP will be decided on a case-by-case basis by the Principal Investigator (or deputy) and Sponsor.

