10.6.10 Prior and Concomitant Therapy

Prior Medication: Prescription or non-prescription drugs, should not be taken within 28 days (or 5 half-lives (whichever is longer)) prior to receiving the first dose of IMP, unless in the opinion of the Investigator and Sponsor's Responsible Physician the medication will not interfere with the study procedures or compromise participant safety. Prescription or non-prescription drugs taken during the 28 days before receiving the first dose of IMP, and the reason for taking them, will be noted in the participant's eCRF.

Inclusion of participants who have taken prior medication will be reviewed on a case-by-case basis in relation to the safety aspects and objectives of this study.

Concomitant Medication: Prescription or non-prescription drugs should not be taken throughout the duration of the study, with the exception of paracetamol (which may be taken as an analgesic to a maximum of 2 grammes (g) in 24 h).

If intake of ANY medication is necessary during the study, the daily dosage, duration and reasons for administration will be recorded in the concomitant medication section of the participant's eCRF.

Prohibited Medications:

28 days prior to first dose (Day 0) to Day 49:

- Prescription and Non-prescription drugs (exception of 2 g per 24 hours of paracetamol).

28 days prior to first dose (Day 0) to 28 days following the third dose on Day 42, i.e. Day 70:

- Antibiotics

Participants requiring antibiotics to treat an infection from Day 0 to Day 49 will be followed for safety but will not receive further doses of IMP.

28 days prior to first dose (Day 0) to Day 84:

- Non-steroidal anti-inflammatory drugs (NSAIDs) (participants will be advised to avoid NSAIDs if possible)
- Steroids
- Immunosuppressants

- Vaccines

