10.9.1.2 Analysis Sets

Safety Set: All randomised participants who receive at least 1 dose of IMP will be included in the Safety Set.

PD Set: All randomised participants who receive at least 1 dose of IMP and have at least one post-baseline antibody concentration will be included in the PD Set.

Per Protocol Set: The Per Protocol Set will be comprised of all participants in the PD Set who comply with the following criteria:

- Do not have an occurrence of vomiting or diarrhoea which may impact the systemic exposure of IMP;
- Do not use a concomitant medication which may impact the immunogenicity results;
- Do not incur a major protocol deviation which may invalidate or bias the immunogenicity results.

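### For a significant protocol violation or poor cooperation, Section 10.5.5 names only withdrawal from the study, so the remaining assessments to Day 84 can be lost for post-dose reasons

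*Combined protocol and SAP*

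**What the plan says.** Section 10.5.5 holds two lists with different consequences. The first opens: "An Investigator will withdraw a participant from the study at any time for any of the following reasons". One of its grounds reads "If a participant incurs a significant protocol violation which impacts on his/her safety or the scientific integrity of the study", and a bracket adds that "this will be discussed on a case-by-case basis with the Sponsor". Another ground covers a participant who does not cooperate enough. No consequence short of withdrawal is named for either.

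The second list covers severe systemic reactions, persistent fever and vaccine-related SAEs. Those participants "will receive no further doses of the study vaccine but will be followed up for safety". Protocol violation is not on this list. Section 10.6.10 applies the same principle to participants who need antibiotics for an infection between Day 0 and Day 49: they "will be followed for safety but will not receive further doses of IMP".

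For anyone withdrawn, Section 10.5.5 says that "every possible effort will be made to perform the evaluations described for the post-study follow-up". Section 10.1 and Table 10.7.1 show what that follow-up is: telephone calls on Days 154 and 224. Section 10.5.5 also says: "The data collected from withdrawn participants will be included in the study report".

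Under Section 10.9.1.2, the Safety Set is everyone randomised and dosed at least once, and the PD Set adds the requirement of one antibody value after baseline. One condition for the Per Protocol Set, drawn from the PD Set, is: "Do not incur a major protocol deviation which may invalidate or bias the immunogenicity results".

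**The concern.** The protocol already separates stopping vaccine from stopping observation, but it does not do so for violations or poor cooperation. Both arise after dosing and can depend on how the participant feels, for example when a prohibited medicine is taken for symptoms. If observation ends for such a reason, the missing values may differ systematically from those observed.

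Two analyses are exposed. The primary endpoint (Section 10.9.1.1) runs to Day 84 and uses laboratory tests, vital signs and physical examination as well as adverse events, and a telephone call cannot supply the first three. The immunogenicity analyses compare groups at each visit. Where a violator's later samples are never taken, they are absent from the PD Set summaries as well as the Per Protocol ones, so comparing the two sets says less about how much deviations matter.

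**Working it through.** The plan gives no figure to reproduce here: Section 10.9.2 states that the sample size has no formal basis. The cohort sizes in Section 10.1 do add up: 9 + 18 + 18 = 45, with 6 + 12 + 12 = 30 on vaccine and 3 + 6 + 6 = 15 on placebo.

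**Step 1. The rules side by side.**

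| Trigger | Section | Dosing | Visits remaining to Day 84 |
|---|---|---|---|
| Significant violation, case by case | 10.5.5, first list | ends with withdrawal | not covered; calls on Days 154 and 224 attempted |
| Insufficient cooperation | 10.5.5, first list | ends with withdrawal | not covered; calls attempted |
| Severe systemic reaction, persistent fever, related SAE | 10.5.5, second list | ends | safety follow-up continues |
| Antibiotics for infection, Day 0 to 49 | 10.6.10 | ends | safety follow-up continues |

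**Step 2. Overlaps.** A related SAE that prevents continued participation meets both lists in Section 10.5.5. Antibiotics are prohibited to Day 70 (Section 10.6.10). Use up to Day 49 is therefore a prohibited-medication deviation and also a stated reason to keep following the participant. Use from Day 50 to Day 70 has no follow-up rule of its own; if it were judged significant, only the withdrawal ground would apply.

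**Step 3. Scheduled data falling after withdrawal.** The post-baseline sampling days come from Table 10.7.2: serum Ig on Days 21, 42 and 84; ALS on Days 7, 28 and 49; safety bloods on Days 7, 21, 28, 42, 49 and 84.

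| Withdrawn | Serum Ig lost | ALS lost | Safety bloods lost |
|---|---|---|---|
| Day 1 | 3 of 3 | 3 of 3 | 6 of 6 |
| Day 22, just after dose 2 | 2 of 3 (Days 42, 84) | 2 of 3 (Days 28, 49) | 4 of 6 (Days 28, 42, 49, 84) |
| Day 43, just after dose 3 | 1 of 3 (Day 84) | 1 of 3 (Day 49) | 2 of 6 (Days 49, 84) |

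In all three rows the Day 70 stool sample is also outstanding. Section 10.3 relies on stool culture to establish that participants are not shedding a genetically modified organism. Withdrawal before any post-baseline antibody sample also costs PD Set membership.

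**Step 4. Effect on safety precision.** Vaccine groups are 6, 12 and 12 (Section 10.1). The numbers lost are assumptions, because the documents give no expected rate. One participant is 1/12 = 8% or 1/6 = 17% of a group. For a finding seen in nobody, the one-sided 95% upper bound is 1 − 0.05^(1/n):

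- n = 6: 1 − 0.05^(1/6) = 39.3%; with 1 lost, 1 − 0.05^(1/5) = 45.1%.
- n = 12: 1 − 0.05^(1/12) = 22.1%; with 2 lost, 1 − 0.05^(1/10) = 25.9%.

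These bounds apply only to findings that a later clinic visit alone could detect.

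**Step 5. Effect on immunogenicity precision.** The half-width of the 95% CI for a log geometric mean, in SD units, is t(0.975, n − 1)/√n. With 1 of 6 lost it goes from 1.049 to 1.242. With 2 of 12 lost it goes from 0.635 to 0.715.

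**The case against.** The strongest reply is that the rule is narrower, and the loss smaller, than a quick reading suggests. Several inferences that a reader might draw are not supported.

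- *That withdrawal is automatic.* It is not. The violation must affect safety or scientific integrity, and each case is discussed with the Sponsor. What remains is that the opening words of the list are mandatory, no criterion guides the discussion, and no lesser consequence is offered.
- *That violators drop out of the analysis sets.* They do not. Membership of the Safety Set depends on dosing alone, and collected data are reported. The headline percentages of participants with adverse events would, on the Safety Set, keep 6 or 12 as denominator, so the Step 4 bounds do not apply to them.
- *That observation from Day 85 to Day 224 stops.* The two calls are still attempted, and Section 10.5.5 provides follow-up of clinically significant abnormalities.
- *That the Per Protocol Set already deals with every violation.* It covers deviations that bias immunogenicity. A violation that endangers the participant is not an analysis-set matter.
- *That anyone taking a medicine for symptoms, or missing a visit, is withdrawn.* Section 10.6.10 allows limited paracetamol, only advises avoiding NSAIDs where possible, and has necessary medication recorded. Nothing classes a missed visit as a significant violation.

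Replacement, also decided case by case, could restore group numbers, but it cannot recover the later values of the person withdrawn.

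What survives is specific. For these two grounds, neither the telephone calls nor any other provision secures the scheduled clinic, laboratory, stool and PD assessments up to Day 84.

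**Conclusion.** The point holds in a limited form. Section 10.5.5 ties a significant violation, once discussed with the Sponsor, and insufficient cooperation to leaving the study, although the protocol elsewhere ends dosing and keeps observing. The loss is of later-visit data to Day 84, not of set membership, data already collected or the late telephone calls.

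The loss per participant follows directly from the schedule. Its effect on precision depends on assumed withdrawals of 1 of 6 or 2 of 12; with none, there is no effect. That the missingness would be informative is a reasonable possibility, not something the documents establish. The trial is small enough for one or two such cases to matter, and the remedy is cheap, so the change is worth making.

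**What to change.** Leave every rule on whether and when dosing stops exactly as it is, including the second list in Section 10.5.5 and the code-break rule in Section 10.6.9. Then:

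1. State in Section 10.5.5 that a participant whose dosing ends because of a protocol violation or non-cooperation is still asked to attend the remaining scheduled safety and PD assessments. The exceptions are withdrawn consent, loss to follow-up, or a documented safety reason against an assessment.
2. State in Section 10.9.1.2 that violations which bias immunogenicity are excluded through the Per Protocol Set only, and that values collected after a violation stay in the PD Set.
3. Reconcile the two lists in Section 10.5.5 for a related SAE, and Sections 10.5.5 and 10.6.10 for antibiotic use. Which rule should govern is for the sponsor and the investigator.

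The cost is an amendment to the wording; the visits are already in the schedule. The small downside is that some off-protocol immunogenicity values enter the PD Set, which the Per Protocol analysis is there to address.

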Participants will be admitted to the Clinical Unit on the morning of Day 21, with assessments performed as per [Table 10.7.1](#). Following a 90-min fast prior to dose administration, participants will receive the second dose, and then continue to fast for a further 90 mins post dose administration; water will be allowed. Following the completion of the 4h post-dose assessments and at the discretion of the Investigator, the participants will be discharged from the Clinical Unit. Participants will return to the Clinical Unit on Day 24 for safety assessments as per [Table 10.7.1](#). For the 7 days following the second dosing visit (Day 22 to Day 28) participants will be required to record their body temperature at home twice a day, i.e. once in the morning and once in the evening (a thermometer and a diary will be provided to record body temperature). Participants will return to the Clinical Unit on Day 28 with the diary and to give a blood sample for the PBMC/ALS assay; assessments will be performed as per [Table 10.7.1](#).

Participants will be admitted to the Clinical Unit on the morning of Day 42, with assessments performed as per [Table 10.7.1](#). Following a 90-min fast prior to dose administration participants will receive the third dose, and then continue to fast for a further 90 mins post dose administration; water will be allowed. Participants will return on Day 45 for safety assessments as per [Table 10.7.1](#). For the 7 days following the third dosing visit (Day 43 to Day 49) participants will be required to record their body temperature at home twice a day, i.e. once in the morning and once in the evening (a thermometer and a diary will be provided to record body temperature). Participants will return to the Clinical Unit on Day 49 with the diary and to give a blood sample for the PBMC/ALS assay; assessments will be performed as per [Table 10.7.1](#).

Participants will return to the Clinical Unit on Day 70 to provide a stool sample for bacteriology. If the stool sample is positive for any *Salmonella* strain at Day 70, it will be presumed to be one of the vaccine strains, and participants will be asked to return to the Clinical Unit to receive a course of antibiotic therapy. Participants who receive a course of antibiotics will be required to provide a repeat stool sample for bacteriology testing on Day 84, to confirm that shedding of the vaccine strains has ceased, as per [Table 10.7.1](#).

Post-Study Follow-Up (Day 85 to Day 224)

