Safety follow-up telephone calls will be performed on Days 154 and 224 following the first dose of study vaccine administration to check the general health of the participant and to review clinically relevant AEs. Clinically relevant adverse events are adverse events that required a visit to a healthcare professional. Assessments will be performed as per [Table 10.7.1](#).

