10.5 Additional Advice and Restrictions for Study Population

10.5.1 Contraception

To prevent pregnancy, female participants of childbearing potential and male participants and their female partner(s) must use 2 reliable forms of contraception, i.e.,

- Condom + Established use of oral, injected or implanted hormonal contraceptive.
- Condom + Intrauterine device.
- Condom + Diaphragm with spermicide.
- True abstinence, when this is in line with the preferred and usual lifestyle of the participant. *[Periodic abstinence (e.g., calendar, ovulation, symptothermal, post-ovulation methods) and withdrawal are not acceptable methods of contraception].*

To prevent exposure of any partner (male or female) during non-vaginal intercourse to the semen from a male participant who has been exposed to the IMP, the following contraception must be used:

- Condom.

The chosen contraception method(s) must be followed from receiving the first dose of IMP until a stool sample tested for presence of the vaccine strains is negative for male participants and at least 2 months after receiving the last dose of IMP for female participants.

Male participants must not have unprotected sexual intercourse with a female who is pregnant or breastfeeding during the study.

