10.7 Safety Variables

10.7.1 Safety Measurements Assessed and Flow Chart

A schedule of study assessments is provided in [Table 10.7.1](#).

Simbec-Orion personnel who have been appropriately trained will carry out study procedures. Where more than 1 procedure is scheduled for the same time-point, the following order of priority will apply:

1. Safety and pharmacodynamic (PD) blood sampling
2. Vital signs and 12-lead ECG (a window of \pm 10 min in relation to the nominal time-point is allowed).
3. Urine collection for urinalysis, urine DOA and urine pregnancy (if applicable)

All baseline assessments will be performed prior to dosing on each dosing day.

Table 10.7.1 Study Flow Chart

	Screening	Treatment Period ¹												Post-Study Follow-Up Telephone Call ²	
		0	1	2	3	4	6	7	10	12	22	32			
Week		0	1	2	3	4	6	7	10	12	22	32			
Day	-28 to -1	0	3	7	14	21	24	28	42	45	49	70	84	154	224
Visit	1	2	3	4	5	6	7	8	9	10	11	12	13	14	15
Visit Window (days)	N/A	+/-0	+/-1	+/-1	+/-1	+/-0	+/-1	+/-1	+/-0	+/-1	+/-1	+/-1	+/-7	+/-7	+/-7
Informed Consent	X														
Inclusion/Exclusion ³	X	X				X		X							
Demographics	X														
Height / Weight / BMI	X												X (weight only)		
Medical History & Concurrent Conditions	X														
Virology Tests	X														
Urine DOA (including Alcohol and Cotinine) ³	X	X ¹¹			X ¹¹			X ¹¹							
Pregnancy ^{3, 4}	X (serum)	X (urine) 11			X (urine) 11			X (urine) 11					X (serum)		
FSH ⁵	X														
Biochemistry ³	X	X ¹¹		X		X ¹¹		X	X ¹¹		X		X		
Haematology ³	X	X ¹¹		X		X ¹¹		X	X ¹¹		X		X		
Urinalysis	X		X			X			X				X		
Vital Signs ⁶	X	X	X	X	X	X	X	X	X	X			X		
Physical Examination	X												X		
General Health Check		X				X			X						
12-Lead ECG	X												X		
Placebo training	X														
Vaccine administration ⁷		X				X			X						

	Screening	Treatment Period ¹												Post-Study Follow-Up Telephone Call ²	
		0	1	2	3	4	6	7	10	12	22	32			
Week		0	1	2	3	4	6	7	10	12	22	32			
Day	-28 to -1	0	3	7	14	21	24	28	42	45	49	70	84	154	224
Visit	1	2	3	4	5	6	7	8	9	10	11	12	13	14	15
Visit Window (days)	N/A	+/-0	+/-1	+/-1	+/-1	+/-0	+/-1	+/-1	+/-0	+/-1	+/-1	+/-1	+/-7	+/-7	+/-7
Twice-Daily Temperature Records ⁸															
Blood culture ⁹															
Stool bacteriology (vaccine strains) ¹⁰											X	(X)			
Administration of antibiotics ¹⁰											(X)				
Blood sample for serum Ig responses ¹¹		X			X			X			X				
PBMC collection for ALS assay ¹¹		X		X				X			X				
Adverse Events		X	X	X	X	X	X	X	X	X	X	X	X	X	X

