Concomitant Medication	X	X	X	X	X	X	X	X	X	X	X	X	X	X	X

Study Flow Chart Footnotes:

All procedures on dosing days (Days 0, 21, 42) are to be completed prior to dosing (except post dosing vital signs and health check for discharge)

¹ The treatment period will be approximately 85 days duration, from the first dosing day (Day 0) until Day 84 (inclusive).

² Post-study follow-up telephone call will be performed on Days 154 and 224 after receiving the first dose of IMP (Day 0).

³ Eligibility will be confirmed prior to dose administration on Day 0, Day 21 and Day 42.

⁴ For female participants only.

⁵ For postmenopausal female participants only

⁶ At Day 0, Day 21, and Day 42, vital signs to be performed pre-dose and at 4 hours post-dose.

⁷ IMP will be administered fasted (90 mins prior to dose administration). Participants will fast for a further 90 mins post each dose administration. Participants in sentinel cohorts will be contacted by telephone approximately 24 hours following the Day 0 dose to assess their safety profile.

⁸ Participants to record body temperature twice daily at home for 7 days post administration of each dose of IMP.

⁹ Blood cultures to be performed to identify vaccine strains only if a participant experiences defined symptoms (e.g., fever greater than 37.8°C, white blood cell (WBC) >20x10⁹ cells/L, respiratory rate >25 breaths per min, pulse rate >130 beats per min (bpm)) or clinically indicated.

¹⁰ Participants will attend the Clinical Unit on Day 70 to provide a stool sample. If the stool sample is positive for any *Salmonella* strain at Day 70, it will be presumed to be one of the vaccine strains, and participants will be asked to return to the Clinical Unit to receive a course of antibiotic therapy, and a repeat stool culture will be obtained on Day 84 to confirm shedding of *Salmonella*, presumed to be one of the vaccine strains, has ceased.

¹¹ Samples to be collected prior to each dosing.

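### The withdrawal rule in Section 10.5.5 points to a follow-up that consists only of telephone calls, so early withdrawals have no scheduled closing safety tests or serology and, before Day 70, no scheduled stool culture.

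*Combined protocol and SAP*

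**What the plan says.** Section 10.5.5 covers participants who are withdrawn, or choose to withdraw, for any reason. For them "every possible effort will be made to perform the evaluations described for the post-study follow-up", with a pointer to Table 10.7.1. Data from withdrawn participants go into the study report.

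Section 10.1 places post-study follow-up after the Day 84 visit and describes its content: "Safety follow-up telephone calls will be performed on Days 154 and 224 following the first dose of study vaccine administration", to ask about general health and adverse events that needed a healthcare visit. The matching columns of Table 10.7.1 are headed "Post-Study Follow-Up Telephone Call".

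Three restrictions are tied to a stool result:

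- **Travel (Section 10.5.4.3):** participants "should not travel outside of the UK until a stool sample cultured for" *Salmonella* is negative.
- **Contraception (Section 10.5.1):** the chosen method continues "until a stool sample tested for presence of the vaccine strains is negative for male participants". Women have a fixed period instead.
- **Sperm donation (Section 10.5.2):** the same end-point as male contraception.

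Section 10.7.1.3.1, on adverse events, calls the post-study follow-up a visit, which does not match the telephone-only schedule.

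**The concern.** A withdrawal rule normally brings the participant back for the closing assessments. Here the pointer passes over the Day 84 clinic visit and lands on the calls that come after it.

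Two things are at stake. The first is the primary endpoint. Section 10.9.1.1 defines it by adverse events, laboratory tests, vital signs and physical examination up to Day 84, and a site that follows the rule exactly will not collect the last three at the point of withdrawal. The second is the shedding check. Section 10.3 explains that the strains are genetically modified and that stool cultures are taken to make sure participants are not shedding. For someone who leaves before Day 70 no culture is scheduled, so three restrictions have no planned end.

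**Working it through.** No power or sample-size figure bears on this point. The check is to compare what the rule points to with what the schedule holds.

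**Step 1. Content of the follow-up columns.** In Table 10.7.1 only the adverse-event and concomitant-medication rows are marked on Days 154 and 224. Laboratory, examination, ECG, serology and stool rows have no mark there.

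**Step 2. Cross-check from blood volumes.** Table 10.7.2 lists draws from Screening to Day 84 only:

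- biochemistry 8 × 3.5 = 28 mL
- haematology 8 × 3.0 = 24 mL
- PBMC/ALS 4 × 64 = 256 mL
- serum Ig 4 × 20 = 80 mL
- total 28 + 24 + 256 + 80 = 388 mL

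This reproduces the stated total exactly, so no blood is planned after Day 84.

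**Step 3. What a participant has on leaving.** Blood days are from Table 10.7.2 and stool days from footnote 10 of Table 10.7.1. Nominal days and attendance at all earlier visits are assumed. Draws on Days 0, 21 and 42 precede that day's dose.

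| Last visit attended | Last safety blood | Last serum Ig | Stool culture |
|---|---|---|---|
| Day 3 | Day 0 | Day 0 | none |
| Day 7 or 14 | Day 7 | Day 0 | none |
| Day 21 or 24 | Day 21 | Day 21 | none |
| Day 28 | Day 28 | Day 21 | none |
| Day 42 or 45 | Day 42 | Day 42 | none |
| Day 49 | Day 49 | Day 42 | none |
| Day 70 | Day 49 | Day 42 | Day 70 |
| Day 84 | Day 84 | Day 84 | Day 70, repeated on Day 84 if positive |

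Three things follow:

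- Day 84 is the only serum Ig sample after the third dose, so every withdrawal before it loses that measurement.
- Physical examination and ECG are marked only at Screening and Day 84, so anyone leaving earlier has neither scheduled after dosing. The dosing-day general health check and repeated vital signs remain.
- A participant leaving before Day 7 has no post-baseline antibody value and falls outside the PD Set of Section 10.9.1.2.

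**Step 4. Size per person.** One early withdrawal from the Cohort 1 active arm is 1/6 = 17% of that arm. From a Cohort 2 or 3 active arm it is 1/12 = 8%.

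**Step 5. A related conflict.** Section 10.6.9 withdraws any participant whose code is broken. Section 10.3 says that participants with a positive *Salmonella* result will be unblinded to the Investigators and the Monitor; the Synopsis says they may be. Section 10.1 requires a repeat stool on Day 84 for those given antibiotics after a positive Day 70 sample. Read together literally, such a participant would move to telephone-only follow-up before that repeat culture.

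**The case against.** **The protocol does not abandon these participants.** A reader might infer that a withdrawn vaccinee gets no tests at all. The documents do not support that. Interim bloods and vital signs taken before withdrawal are kept and reported. Section 10.5.5 follows clinically significant abnormalities until they are acceptable. Section 10.9.1.1 allows laboratory tests, vital signs and physical examination for cause from Day 85 to Day 224. This objection stands, and it limits the point to assessments that are *scheduled*. None of these provisions supplies serology or a shedding check.

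**Key reactors may not be withdrawn.** A reader might infer that withdrawals are concentrated among people with adverse reactions. No section says so. Section 10.5.5 keeps participants with a severe systemic reaction, a persistent febrile reaction or a related SAE under safety follow-up without further doses, and Section 10.6.10 does the same for those needing antibiotics between Day 0 and Day 49. They are a separate group. A serious or intolerable event that prevents continuing is one listed reason for withdrawal among several. This objection also stands.

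**It may be only a wording slip.** The reference to a follow-up visit in Section 10.7.1.3.1 suggests that the term is used loosely. That may explain the cause, but a site following Table 10.7.1 would still make telephone calls.

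**The Day 70 unblinding may be outside the code-break rule.** Section 10.6.9 is mainly about emergencies and adverse events. However, its withdrawal sentence covers any code break and makes no exception for a positive stool.

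**Conclusion.** The point holds for scheduled assessments. As written, the rule gives a participant withdrawn before Day 84 no scheduled closing laboratory tests, physical examination, ECG or serum Ig. It gives one withdrawn before Day 70 no scheduled stool culture, while three restrictions depend on a negative one. What is lost is the data after the last attended visit, not all objective safety data.

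The number affected cannot be stated. The protocol gives no dropout rate. A reader might apply an assumed rate to all 45 participants, but that count would include the 3 + 6 + 6 = 15 placebo recipients, people lost to follow-up whom no visit would reach, and people who leave after Day 70 or Day 84 with some or all of these assessments done. The 17% and 8% describe one withdrawal in an active arm and do not predict how many will occur.

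The conclusion rests on the text of Sections 10.1 and 10.5.5, the footnotes of Table 10.7.1 and the volumes in Table 10.7.2. Only the Day 84 position of the examination and ECG marks rests on the layout of the flow chart alone. The change should be made: it is cheap, and samples not taken at withdrawal cannot be recovered later.

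**What to change.** 1. In Section 10.5.5, replace the cross-reference with the Day 84 safety and serology assessments, done at an early-withdrawal visit with the participant's agreement. Add stool bacteriology for anyone without a stool result. Keep the Day 154 and Day 224 calls.
2. Add an Early withdrawal column to Table 10.7.1, and correct the reference to a follow-up visit in Section 10.7.1.3.1.
3. State the timing of that stool relative to the last dose. The planned sample falls 70 − 42 = 28 days after the third dose, and a sample at withdrawal could fall much sooner. State also how the existing provisions for a positive result apply to it. Both are for the sponsor to decide.
4. Reconcile the Synopsis and Sections 10.1, 10.3 and 10.6.9, so that unblinding for a positive Day 70 stool does not remove a participant before the Day 84 repeat culture that the protocol already requires.
5. Label these results as an early-withdrawal time-point in the summaries. Section 10.9.1.3 uses only scheduled values after vaccination, and Section 10.9.1.3.3 tabulates laboratory data by protocol-defined time-point, so without this the results could be left out or mixed with Day 84.

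**Cost.** Protocol wording, one flow-chart column, and one clinic visit per reachable early withdrawal, with any further contact that a positive stool brings. The blood needed is the Day 84 draw, 3.5 + 3.0 + 20 = 26.5 mL, taken in place of Day 84, so the planned total stays within 388 mL.
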